2.2.2 Secondary objective endpoints and estimands

Table 2-2: Secondary objective

Objectives	Endpoints/estimands
Secondary objective	Secondary endpoints
To investigate long-term efficacy of BRV in pediatric study participants with CAE or JAE	
Absence seizure freedom within 4 days prior to or during the 1-hour EEG at each applicable visit up to Month 24 
Estimand:
 
Population: the study participant population as defined in the protocol-specified inclusion/exclusion criteria reflecting the target patient population.Study participant-level outcome: seizure freedom response while awake on 1-hour EEG at each applicable visit up to Month 24.Intercurrent event handling: The intercurrent event of concomitant use of any AED, including benzodiazepines, within 4 days prior to or during the 1-hour EEG is handled in the definition of the participant-level variable implementing a composite strategy in which receiving any concomitant AED, including benzodiazepines, within 4 days prior to or during the 1-hour EEG is counted as nonresponse (ie, considered as having absence seizures during the EEG).Population-level summary measure: percentage of study participants free from absence seizures.

Table 2-2: Secondary objective

To investigate long-term efficacy of BRV in pediatric study participants with CAE or JAE	
 Absence seizure freedom based on diary over the Evaluation Period truncated at Month 24 and by each applicable 3-month time interval up to Months 22-24 
Estimand
 
 Population: the study participant population as defined in the protocol-specified inclusion/exclusion criteria reflecting the target patient population. Study participant-level outcome: seizure freedom response on diary over the Evaluation Period truncated at Month 24 and by each applicable 3-month time interval up to Months 22-24. Intercurrent event handling: The intercurrent event of concomitant use of any AED, including benzodiazepines, during each applicable 3-month period is handled in the definition of the participant-level variable implementing a composite strategy in which receiving any concomitant AED, including benzodiazepines, in the 3-month period or during the visit is counted as nonresponse (ie, considered as having absence seizures). The intercurrent event of diary completion during each applicable period is handled in the definition of the participant-level variable implementing a composite strategy in which completing less than 80% of diaries during the 3-month period is counted as nonresponse (ie, considered as having absence seizures). Population-level summary measure: percentage of study participants free from clinical absence seizures.
Secondary objective	Other endpoints
To investigate long-term efficacy of BRV in pediatric study participants with CAE or JAE	
 Consecutive absence seizure freedom in 6-month periods based on EEG up to Month 24 Consecutive absence seizure freedom in 6-month periods based on diary up to Month 24

AED=antiepileptic drug, BRV=brivaracetam, CAE=childhood absence epilepsy, EEG=electroencephalogram, JAE=juvenile absence epilepsy, SAE=serious adverse event, TEAE=treatment-emergent adverse event

2.2.3 Tertiary/exploratory object endpoints

Table 2-3: Tertiary/exploratory objective

Objectives	Endpoints/estimands
To investigate the long-term effect of	
 CFB to each applicable visit in the EpiTrack Junior scores (for study participants 6 to <18 years old)

Table 2-3: Tertiary/exploratory objective

Objectives	Endpoints/estimands
BRV on behavior, cognition, and quality of life in pediatric study participants with CAE or JAE	
CFB to each applicable visit in PedsQL Generic Core scale scores from the study participant self-reports (separate questionnaires for participants age in years: 5 to \leq7, 8 to \leq12, 13 to \leq17 years)CFB to each applicable visit in PedsQL Generic Core scale scores from the parent proxy reports (separate questionnaires for participants age in years: 2 to \leq4, 5 to \leq7, 8 to \leq12, 13 to \leq17 years)

BRV=brivaracetam, CAE=childhood absence epilepsy, CFB=change from baseline, JAE=juvenile absence epilepsy, PedsQL=Pediatric Quality of Life

2.3 Study design and conduct

2.3.1 Overall design

EP0132 is a Phase 3, open-label, single-arm, multicenter, long-term follow-up (LTFU) study to evaluate the safety, tolerability, and efficacy of BRV in pediatric study participants with CAE or JAE. The study is designed for study participants in the age range of 2 to 26 years of age, who have participated in study N01269 and qualify for entry into EP0132.

Upon enrollment, eligible study participants will enter the Evaluation Period and start on a BRV dose of 100mg/day (or equivalent dose of 2mg/kg/day for study participants weighing less than 50kg). The dose may be adjusted after 3 days in the range of 50 to 200mg/day (or equivalent dose of 1 to 4mg/kg/day for study participants weighing less than 50kg) based on the individual needs.

The EV is the first study visit and is equivalent to last study visit of the core study (N01269). Within each year of study participation during the Evaluation Period, Minimal Evaluation Visits (MEVs) will be performed at Months 3 and 9, Full Evaluation Visits (FEVs) will be performed at Month 6, and Yearly Evaluation Visits (YEVs) will be performed at Month 12. At any time, the study participant may have an Unscheduled Visit (UV) if the Investigator or the participant and/or parent(s)/legal representative(s) consider it necessary. For study participants who continue in the study until it ends, the Evaluation Period will last from the EV to the FV. For study participants who prematurely discontinue the study, the Evaluation Period will last from the EV until EDV.

For study participants who transition to another BRV study or a managed access program or similar type of program or who convert to commercial BRV (if, when, and where available), the FV instead of the EDV will need to be completed; however, down-titration and the Safety Visit (SV) will not be applicable.

For study participants who will discontinue BRV treatment following the EDV or FV and a dose of >1 mg/kg/day (>50 mg/day for study participants with body weight ≥ 50 kg) is reached at the EDV or FV respectively, the BRV dose will be reduced by a maximum of half the dose every week for a maximum of 4 weeks until a dose of 1mg/kg/day (50mg/day for study participants with body weight >50 kg) is reached (Down-Titration Period). A Down-Titration Visit (DTV) will be performed at the end of the Down-Titration Period, and study drug will be discontinued at the DTV. After 2 weeks free of study drug (Safety Period), study participants will complete

the SV. Otherwise, for study participants who will discontinue BRV treatment following the EDV or FV and a dose of 1mg/kg/day (50mg/day for study participants with body weight >50kg) is reached at the EDV or FV respectively, down titration will not be applicable; after 2 weeks free of study drug (Safety Period), study participants will complete the SV.

2.3.2 Study treatment

Brivaracetam (tablet [10, 25, or 50mg] or oral solution [10mg/mL]) will be administered twice per day in equal doses in the range of 50 to 200mg/day (or equivalent doses of 1 to 4mg/kg/day for study participants weighing less than 50kg, not to exceed 200mg/day [or equivalent dose of 4mg/kg/day for participants weighing less than 50kg].

2.3.3 Seizure data collected

2.3.3.1 EEG

For all study participants, data from a 1-hour EEG with hyperventilation (HV) test will be collected at FEVs, YEVs, and the EDV or FV (as applicable). Each of these EEGs will be locally read. The awake time from the EEG will be analyzed for absence seizures. The awake and asleep time from the EEG will be analyzed for other seizure types. The investigator/designated EEG reader will attempt to keep the study participant awake for the duration of the 1-hour EEG, and a minimum of 30 minutes of awake time is required for the EEG to be evaluable.

2.3.3.2 Daily seizure diaries

Data from daily seizure diaries will be collected during the Evaluation Period (from the EV until the EDV or FV as applicable) and the Down-Titration Period for participants who down-titrate. Study participants will record all types of seizures that occur in their diaries and will complete the diaries after each seizure or at least once a day.

2.4 Determination of sample size

No formal sample size calculation was performed for this study. Approximately 140 study participants may enroll in this study, based upon the rollover expectations from N01269 into EP0132.

3 DATA ANALYSIS CONSIDERATIONS

3.1 Endpoints and statistical measures

Table 3-1: Study endpoints and statistical measures

Objective	Endpoint	Statistical measure(s)
Primary objective	Primary endpoint	
To investigate the long-term safety and tolerability of BRV in pediatric study participants with CAE or JAE	TEAEs	Incidence of TEAEs
	TEAEs leading to discontinuation of study drug	Incidence of TEAEs leading to discontinuation of study drug

Table 3-1: Study endpoints and statistical measures

Objective	Endpoint	Statistical measure(s)
Primary objective	Secondary endpoints	
To investigate the long-term safety and tolerability of BRV in pediatric study participants with CAE or JAE	SAEs	Incidence of serious TEAEs
	Study drug-related TEAEs	Incidence of study drug-related TEAEs
Primary objective	Other endpoints	
To investigate the long-term safety and tolerability of BRV in pediatric study participants with CAE or JAE	TEAEs requiring a change in BRV dose	Incidence of TEAEs requiring a change in BRV dose
	Maximum intensity TEAE experienced (mild, moderate, and severe)	Incidence of TEAEs by maximum intensity experienced
	Drug-related serious TEAEs	Incidence of drug-related serious TEAEs
	Fatal AEs	Incidence of fatal AEs
	TEAEs by maximum relationship (related and not related to BRV)	Incidence of TEAEs by maximum relationship to study drug
	SAEs by maximum relationship (related and not related to BRV)	Incidence of serious TEAEs by maximum relationship to study drug
	Non-absence seizures based on 1-hour EEG	Incidence of non-absence seizures based on EEG
	Non-absence seizures based on diary	Incidence of non-absence seizures based on diary
	CFB to each applicable visit in safety laboratory tests	Summary statistics of individual visit values and corresponding CFB to each visit

Table 3-1: Study endpoints and statistical measures

Objective	Endpoint	Statistical measure(s)
	CFB to each applicable visit in ECG parameters	Summary statistics of individual visit values and corresponding CFB to each visit
	ECG findings at each applicable visit	Incidence of ECGs which are abnormal clinically significant and abnormal not clinically significant
	Physical and neurological examinations findings at each applicable visit	Shift from Baseline neurological examinations findings which are abnormal clinically significant and abnormal not clinically significant. Physical examinations findings will be listed only
	Psychiatric and mental status at each applicable visit	Shift from Baseline psychiatric and mental status which are abnormal clinically significant and abnormal not clinically significant
	CFB to each applicable visit in vital signs (blood pressure, pulse rate, body temperature)	Summary statistics of individual visit values and corresponding CFB to each visit
	CFB to each applicable visit in body weight and height	Summary statistics of individual visit values and corresponding CFB to each visit
Secondary objective	Secondary endpoints	
To investigate long-term efficacy of BRV in pediatric study participants with CAE or JAE	Absence seizure freedom within 4 days prior to or during the 1-hour EEG at each applicable visit, up to Month 24	Percentage of study participants free from absence seizures while awake on 1-hour EEG with

Table 3-1: Study endpoints and statistical measures

Objective	Endpoint	Statistical measure(s)
		no concomitant use of AEDs within 4 days prior to or during the 1-hour EEG
	Absence seizure freedom based on diary over the entire Evaluation Period, truncated at Month 24, and by 3-month time intervals up to Month 24	Percentage of study participants free from absence seizures based on diary during Evaluation Period and during each 3-month interval
Secondary objective	Other endpoints	
To investigate long-term efficacy of BRV in pediatric study participants with CAE or JAE	Consecutive absence seizure freedom in 6-month periods based on EEG up to Month 24	Percentage of study participants free from absence seizures in consecutive 6-month periods based on EEG
	Consecutive absence seizure freedom in 6-month periods based on diary up to Month 24	Percentage of study participants free from absence seizures in consecutive 6-month periods based on seizure diary
Tertiary/Exploratory	Other endpoints	
To investigate the long-term effect of BRV on behavior, cognition, and quality of life in pediatric study participants with CAE or JAE	CFB to each applicable visit in the EpiTrack Junior scores (for study participants 6 to <18 years old)	Summary statistics of individual visit values and corresponding CFB to each visit
	CFB to each applicable visit in PedsQL Generic Core scale scores from the study participant self-reports (separate questionnaires for participants age in years: 5 to ≤7, 8 to ≤12, 13 to ≤17 years)	Summary statistics of individual visit values and corresponding CFB to each visit

Table 3-1: Study endpoints and statistical measures

Objective	Endpoint	Statistical measure(s)
	CFB to each applicable visit in PedsQL Generic Core scale scores from the parent proxy reports (separate questionnaires for participants age in years: 2 to ≤ 4 , 5 to ≤ 7 , 8 to ≤ 12 , 13 to ≤ 17 years)	Summary statistics of individual visit values and corresponding CFB to each visit

AE=adverse event, AED=antiepileptic drug, BRV=brivaracetam, CAE=childhood absence epilepsy, CFB=change from baseline, ECG=electrocardiogram, EEG=electroencephalogram, JAE=juvenile absence epilepsy, PedsQL=Pediatric Quality of Life Inventory, SAE=serious adverse event, TEAE=treatment-emergent adverse event

3.2 General presentation of summaries and analyses

Statistical analysis and generation of tables, figures, study participant data listings, and statistical output will be carried out using SAS® Version 9.3 or higher. Descriptive statistics, such as the number of study participants with available measurements (n), mean, standard deviation (SD), median, minimum value, and maximum value for quantitative variables, and counts and percentages for categorical variables, will be provided. Unless otherwise noted, the denominator for percentages will be based on the set of study participants in the specified analysis set with at least 1 assessment at the time point or at least 1 assessment during the time interval being summarized.

Decimal places for descriptive statistics will always apply the following rules (with the exception of PK data):

- “ n ” will be an integer
- Mean, SD, and median will use 1 additional decimal place compared to the original data.
- Minimum and maximum will have the same number of decimal places as the original value.

The individual PK concentrations will be reported to 3 significant figures in the listing. The descriptive statistics will be rounded to 4 significant figures for the mean, geometric mean, median, SD, and confidence interval (CI), to 1 decimal place for geometric coefficient of variation and to 3 significant figures for the min, max.

Unless otherwise noted, all percentages will be displayed to 1 decimal place. No percentage will be displayed for zero counts, and no decimal will be presented when the percentage is 100%.

Unless otherwise specified (eg, for Baseline values), all outputs are based on data collected in EP0132 only, and do not include data collected in N01269. Data sources for the EP0132 EV are specified in [Section 3.3.6](#).

All outputs will be produced by actual syndrome (CAE/JAE) as reported in N01269 and for all participants. Adverse event outputs will be produced for the Evaluation Period and 3-month periods within the Evaluation Period. Selected outputs may also be produced by modal dose, maximum BRV dose, exposure duration, and 3-month periods during the Evaluation Period.

Statistical outliers are defined as values that are discordant with other values and are clinically implausible. Exclusion of outliers from an analysis requires thorough justification based on statistical and clinical grounds. In such cases, unless otherwise specified, the analysis will be run both with and without the values. Any outliers will be reviewed during data evaluation meetings (DEM). Study participant data listings will be provided and will present source data and key derived variables for statistical analyses, outliers excluded from analysis will be clearly marked.

Selected summary tables and figures may be presented over all study participants and by COVID-19 period (during pandemic and post pandemic). COVID-19 periods are defined in [Section 3.3.4](#).

Listings will specify the study participant number, actual syndrome (CAE/JAE), and where relevant, gender, age in years at EP0132 EV, race, and weight in kg at EP0132 EV. Only observed values will be displayed unless otherwise specified. For instance, partial dates will only display the observed data.

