9.2 General statistical considerations

All computations for the non-PK analyses will be performed using SAS® version 9.3 or later (SAS Institute, NC, USA).

Descriptive statistics, such as the mean, standard deviation, median, minimum value, and maximum value for quantitative variables, and counts and percentages for categorical variables, will be provided. Key supporting data will be provided in data listings. No hypothesis testing will be conducted.

All outputs will be produced for all participants. Adverse event outputs will be produced for the Evaluation Period, 3-month periods within the Evaluation Period, the Down-Titration Period, and the Safety Period. Selected outputs may also be produced by modal dose, maximum BRV dose, exposure duration, 3-month periods during the Evaluation Period and study period.

Statistical outliers are defined as values that are discordant with other values and are clinically implausible. Exclusion of outliers from an analysis requires thorough justification based on statistical and clinical grounds. In such cases, unless otherwise specified, the analysis may be run both with and without the values. Any outliers will be reviewed during the data evaluation meeting. Study participant data listings will be provided and will present source data and key derived variables for statistical analyses, outliers excluded from analysis will be clearly marked.

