9.4 Planned safety and other analyses

9.4.1 Safety analyses

Adverse event summary tables will be presented over the Evaluation Period, by 3-month intervals during the Evaluation Period, the Down-Titration Period, and Safety Period for the SS.

All safety variables will be analyzed by descriptive methods on the SS. Adverse events will be coded using the Medical Dictionary for Regulatory Activities (MedDRA®). Treatment-emergent AEs (TEAEs) will be summarized by MedDRA System Organ Class and Preferred Term. The incidence of TEAEs, SAEs, TEAEs leading to discontinuation, and study treatment-related TEAEs will also be summarized.

Other safety variables, including laboratory values, vital signs, weight and height will be summarized by scheduled visit. All PCST abnormalities for laboratory values, vital signs and weight will be summarized by scheduled visit and listed. All ECG findings, as well as physical and neurological examination findings and psychiatric/mental status, will be listed.

The nonabsence seizure incidence will be summarized descriptively based on EEG and participant diary at each scheduled visit.

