3.3.2 Study periods

For reporting purposes, the Evaluation Period will last from the date of first dose in EP0132 until the FV inclusive, or from the date of first dose in EP0132 until the EDV inclusive for study participants who prematurely discontinue the study. The Evaluation Period may be truncated at the Month 24 YEV for the reporting of the absence seizure freedom based on seizure data (diary and EEG). It is expected that the first dose in EP0132 will be taken in the evening of the EV. For

participants who complete the study at the FV, the Overall Period will include the Evaluation Period only. Otherwise, for participants who are not required to down-titrate as a dose of 1mg/kg/day (50mg/day for study participants with body weight $>50\text{kg}$) is reached at the FV or EDV, the Overall Period will include the Evaluation Period and Safety Period. Otherwise, the Overall Period will include the Evaluation Period, Down-Titration Period and Safety Period.

For study participants who discontinue BRV treatment following the EDV or FV and a dose of $>1\text{mg/kg/day}$ ($>50\text{mg/day}$ for study participants with body weight $\geq 50\text{kg}$) is reached at the EDV or FV respectively, the BRV dose will be reduced by a maximum of half the dose every week for a maximum of 4 weeks until a dose of 1mg/kg/day (50mg/day for study participants with body weight $>50\text{kg}$) is reached (Down-Titration Period). A DTV will be performed at the end of the Down-Titration Period, and study drug will be discontinued at the DTV. Otherwise, for study participants who will discontinue BRV treatment following the EDV or FV and a dose of 1mg/kg/day (50mg/day for study participants with body weight $>50\text{kg}$) is reached at the EDV or FV respectively, down titration will not be applicable.

After 2 weeks free of study drug (Safety Period), study participants will complete the SV.

The definitions of the Evaluation, Down-Titration, Safety Follow-up, and Overall Periods are provided in [Table 3-2](#). Adverse events are assigned to a study period based on the date of onset. All other measurements are assigned based on the date of assessment.

Table 3-2: Definition of study periods

Period	Definition	Algorithmic rule

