10.2 Adverse events

Adverse events will be summarized as reported on the EP0132 eCRF without integration of events from the N01269 analysis database. Any AEs that are ongoing at the time of entry into EP0132 will be entered on the EP0132 AE eCRF.

All AEs in this study will be classified as pre-treatment or treatment-emergent. In the following definitions, first dose of BRV refers to the first dose in EP0132. Pre-treatment AEs are defined as AEs which had an onset date prior to the first dose of BRV. Treatment-emergent adverse events are defined as AEs that had onset on or after the day of first dose of BRV. All summaries of TEAEs will be based on the SS. Summaries of TEAEs will be produced for the Overall Period, the Evaluation Period, and for each 3-month period in the Evaluation Period (as defined in [Table 3-3](#)), more details on the requirements of each period for each summary are provided in [Section 10.2.1](#).

For the reporting of UCB plain language summaries (PLS) additional summaries of TEAEs will be reported based on the SS. These will only be produced for the Overall Period.

For all summaries (with the exception of TEAEs leading to permanent discontinuation of study drug) the intercurrent event of treatment discontinuation is handled by using a while-on-treatment strategy where observation ends 14 days after treatment is stopped. Thus summaries will include all TEAEs with onset on or after the day of the first dose of BRV up to and including the date of last dose of BRV + 14 days, where missing or partial date of last dose is handled as described in [Section 4.1.4.5](#).

The standard AE eCRF has the outcome of “worsened” to be used when there is an increase in the intensity of an AE. The definition of “worsened” is when the AE is still present but at a heightened intensity. The eCRF instructions dictate to complete a new AE screen with the event term of the worsened event.

Note that the outcome of “worsened” is not allowed terminology within the CDISC standards. In the SDTM.AE, the data is mapped to the outcome “Not Recovered/Not Resolved”. The outcome of “Worsened” will be kept in SDTM.SUPPAE.

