10.2.1 AE summaries

An overall summary of TEAEs will provide the number and percentage of study participants with at least one: TEAE, serious TEAE, TEAE requiring dose change, drug-related TEAE, severe TEAE, TEAE leading to permanent discontinuation of study drug, AE leading to death (based on the All Participants Screened Set), and TEAE leading to death. This will be produced for the Overall Period and the Evaluation Period. Additionally, this summary will be presented by modal dose category for the Evaluation Period and for each 3-month period in the Evaluation Period.

Treatment-emergent AEs requiring a dose change will be identified from the AE eCRF where “Action Taken with Study Medication” is “Dose reduced” or “Dose increased”.

All AEs will be summarized overall and by MedDRA primary system organ class (SOC) and MedDRA preferred term (PT). The number and percentage of study participants experiencing each event at least once will be summarized. All summaries will be sorted alphabetically by SOC and by incidence of AEs within PTs, starting with the highest incidence overall. Only the first occurrence of a TEAE of a particular PT will be included in incidence calculations, but all occurrences of TEAEs of the same PT will be included in counts of TEAEs. All summaries will be produced for the Overall Period, Evaluation Period and for each 3-month period in the Evaluation Period except for the incidence of TEAEs leading to permanent discontinuation of study drug which will not be produced for the Overall Period.

The following summaries will be provided:

- Incidence of TEAEs
- Incidence of TEAEs leading to permanent discontinuation of study drug
- Incidence of serious TEAEs
- Incidence of TEAEs by relationship
 - Relationship is related/not related to study drug and is decided by the study investigator.
- Incidence of TEAEs by maximum relationship.
 - Related to study drug is considered more significant than not related to study drug ie, if a study participant has experienced the same TEAE on more than one occasion, where on at least one of the occasions it was considered to be related to the study drug, the maximum relationship is related.
- Incidence of TEAEs not exclusively related to COVID-19 vaccination
 - These will be identified as TEAEs where “Is the Event Related to a COVID-19 Vaccination” is answered “No” on the AE eCRF
- Incidence of TEAEs by maximum intensity

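### The SAP omits, without declaring it, the adverse event tables that the protocol plans for the Down-Titration and Safety Periods, so participant incidence in those periods is not reported

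*SAP*

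**What the plan says.** The protocol makes the commitment twice. Section 9.2: "Adverse event outputs will be produced for the Evaluation Period, 3-month periods within the Evaluation Period, the Down-Titration Period, and the Safety Period". Section 9.4.1, for summary tables on the Safety Set: "Adverse event summary tables will be presented over the Evaluation Period, by 3-month intervals during the Evaluation Period, the Down-Titration Period, and Safety Period".

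The SAP is narrower. Section 3.2: "Adverse event outputs will be produced for the Evaluation Period and 3-month periods within the Evaluation Period". Section 10.2: "Summaries of TEAEs will be produced for the Overall Period, the Evaluation Period, and for each 3-month period in the Evaluation Period". Section 10.2.1, for the tables by system organ class and preferred term: "All summaries will be produced for the Overall Period, Evaluation Period and for each 3-month period in the Evaluation Period". It makes one exception, the incidence of "TEAEs leading to permanent discontinuation of study drug which will not be produced for the Overall Period".

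The SAP still defines the Down-Titration and Safety Periods algorithmically (Table 3-2) and assigns each AE to a period by onset date (3.3.2). For participants who go through both later phases, 3.3.2 pools them with treatment: "Otherwise, the Overall Period will include the Evaluation Period, Down-Titration Period and Safety Period".

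SAP 3.12, which collects departures from protocol-defined analyses, has three entries: concomitant antiepileptic drugs, truncation of seizure-freedom data at Month 24, and the EpiTrack Junior age correction. None concerns AE periods. The version history presents the new text on AE periods in 10.2 and 10.2.1 as clarification, although it labels other entries as changes from protocol.

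**The concern.** Long-term safety and tolerability is the primary objective. Protocol 4.2 explains the post-treatment observation window for the primary TEAE endpoint by the wish to capture events after brivaracetam ends. Dose reduction and the drug-free fortnight are clinically different from stable treatment, and the protocol planned to show them separately.

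Under the SAP a reader sees these events only when pooled with the whole treatment phase. At stake is a simple descriptive result: of the participants who reduced or stopped the drug, how many had a TEAE, a serious TEAE or a drug-related TEAE in that phase. The departure is also undeclared, so a reader who relies on SAP 3.12 would not know that the planned tables had gone.

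**Working it through.** The plan gives no figure to reproduce. The check compares the texts and then asks whether the missing result can be rebuilt from what remains.

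**Step 1. Periods with AE tables.**

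| Period | Protocol 9.2, 9.4.1 | SAP 3.2 | SAP 10.2, 10.2.1 |
|---|---|---|---|
| Evaluation | yes | yes | yes |
| 3-month within Evaluation | yes | yes | yes |
| Down-Titration alone | yes | no | no |
| Safety alone | yes | no | no |
| Overall (pooled) | no | no | yes |

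Two planned presentations are gone and one has been added. SAP 3.2 also disagrees with 10.2 and 10.2.1, because it omits the Overall Period.

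**Step 2. Can Overall minus Evaluation recover the result?** SAP 10.2.1 counts a participant once per preferred term for incidence but includes every occurrence in event counts. Take two hypothetical participants and one preferred term. A has the event during Evaluation and again in the Safety Period. B has it for the first time during down-titration.

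| | Overall | Evaluation | Difference | True number after Evaluation |
|---|---|---|---|---|
| Events | 3 | 1 | 3 − 1 = 2 | 2 |
| Participants | 2 | 1 | 2 − 1 = 1 | 2 |

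Event counts subtract correctly, though the difference merges the two later periods. Participant counts do not: A disappears.

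**Step 3. Denominator.** TEAE summaries use the Safety Set (SAP 10.2). Participants who move to another brivaracetam study, an access programme or commercial drug have no down-titration and no Safety Visit (Protocol 4.1; SAP 2.3.1). They remain in the Overall Period denominator although they never enter either later phase. By contrast, SAP 3.3.3 includes participants in a 3-month AE summary only if their Evaluation Period reaches it. No such rule exists for the two later periods.

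**Step 4. Other sources.** The discontinuation table by system organ class and preferred term has no Overall Period version, so it does not cover these phases. A discontinuation row remains in the overall TEAE summary, which is produced for the Overall Period. SAP 10.2.2 lists all AEs with onset date and dose at onset, but study period is not among the fields it names.

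**Step 5. Size, by assumption only.** The documents do not say how many will down-titrate; about 140 may enrol. Suppose 6 participants have an event in one of the periods:

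- 20 enter: 6/20 = 30.0%
- 40 enter: 6/40 = 15.0%
- 80 enter: 6/80 = 7.5%
- Effect on an Overall Period percentage with 140 in the denominator: at most 6/140 = 4.3 percentage points, and as little as 0 if all six already had a qualifying event during Evaluation.

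This range shows how dilution works. It is not an estimate for this trial.

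**The case against.** The best defence is that nothing is hidden and no estimand is harmed. The primary estimand is TEAE incidence with observation ending 14 days after treatment stops, and the Overall Period tables with the cut-off at last dose plus 14 days cover that window. No objective or estimand asks for incidence by phase. The study is descriptive, and the protocol leaves detail to the SAP. Event counts can be subtracted, AEs are listed, and the version history shows which periods were chosen.

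Most of this stands. A reader might infer that withdrawal-phase events go unreported, or that the primary safety result is compromised. The documents support neither: the events are in the pooled tables and the listings, and the primary estimand is intact.

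Two things remain. Leaving detail to the SAP does not extend to removing tables that the protocol says will be produced, and a note of clarification is not a declared change. And subtraction gives events, not participants at risk.

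Reinstatement also needs more than a switch in the programs. In Table 3-2 the Safety Period of participants who down-titrate starts the day after the Down-Titration Visit, with no rule if that visit is missed, although the Down-Titration rule foresees this. A late Safety Visit would also carry the Safety Period past the 14-day TEAE cut-off.

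**Conclusion.** The discrepancy is established by the text and rests on no assumption. Two sets of protocol-planned AE tables are absent from the SAP, no other section restores them, and SAP 3.12 is silent. The consequence is limited but real: participant incidence during dose reduction and after stopping, among those who entered each period, is neither reported nor derivable from the planned tables. It would have to be rebuilt from listings by reapplying the period definitions.

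The point should be corrected, but it does not threaten the primary analysis. It is tempting to attach a specific degree of dilution. The documents do not support one, because the number who will down-titrate is not given; only an explicitly assumed range can be shown.

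**What to change.** - In SAP 10.2 and 10.2.1, reinstate summaries of TEAEs, serious TEAEs and drug-related TEAEs for the Down-Titration Period and for the Safety Period, with participants who entered the period as the denominator.
- Apply the cut-off at last dose plus 14 days to the Safety Period table.
- In Table 3-2, state when the Safety Period starts if the Down-Titration Visit is missed.
- Align SAP 3.2 with 10.2 and 10.2.1, including the Overall Period.
- If the sponsor prefers to keep the omission, enter it in SAP 3.12 as a change from Protocol 9.2 and 9.4.1, with the reason.

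The cost is modest. No new data are needed, and AEs are already assigned to periods by onset date. Because outputs are shown for CAE, JAE and all participants, two periods mean 2 × 3 = 6 extra columns in each of the three summaries. The declaration alone is a short entry in 3.12.
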